2.1 OBJECTIVES AND SCIENTIFIC AIMS

Primary objective:

- To determine non-inferiority of ABPI when compared to BioSentry in reducing the rate of iatrogenic pneumothorax during the routine observation stay within 2 hours following image guided lung biopsy.

Secondary objective:

- To evaluate ABPI and BioSentry in reducing the rate of iatrogenic pneumothorax during the routine observation stay within 2 hours following image guided biopsy in a per-protocol analysis.
- To evaluate ABPI and BioSentry in reducing the rate of chest tube placement for pneumothorax up to two weeks following lung biopsy.
- To evaluate ABPI and BioSentry in reducing the rate of delayed pneumothorax up to two weeks following lung biopsy.

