Pneumothorax (appendix 20.2.1) will be mainly defined based on post procedure chest x-rays. Any discernible pneumothorax on chest x-rays is considered a positive finding. Minuscule pneumothorax (a tiny film of air) which is sometimes seen on the last set of CT images of a biopsy procedure after the introducer needle is removed is not considered a positive finding. This is due to high sensitivity of CT imaging. Any pneumothorax larger than minuscule on CT images is considered a positive finding.

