10.0 EVALUATION DURING TREATMENT/INTERVENTION

After the biopsy, the patient will be transferred to the recovery unit. Two chest radiographs will be obtained immediately and 2 hours after the procedure as per standard of care. Additional radiographs may be obtained when indicated as per standard of care.

Patients with no or with a small stable asymptomatic pneumothorax on the post procedure chest radiographs will be discharged.

A chest tube will be placed for patients with a large pneumothorax, patients with a pneumothorax that is increasing in size rapidly, or symptomatic patients with any pneumothorax. Patients who undergo chest tube placement will generally be admitted for overnight observation. Chest tubes will be removed when there is no longer an air leak and the radiographic appearance remains stable for 2 hours with the chest tube clamped. This happens the next day of the biopsy for the majority of cases. Patients will be discharged home once the chest tube is removed. At the time of discharge all patients will be given contact information and will be asked to call back with any symptoms that might be related to delayed pneumothorax. In addition, patients who did not have a chest tube placed will be followed up with a phone call within two weeks for assessment of delayed pneumothorax, a rare occurrence. The only step in the peri, intra and post procedural management of these patients which is not a part of standard of care is the one-week post procedure phone call. All other steps are within standard of care. Any treatment as a consequence to the follow-up phone call is also a part of standard of care.

In case any of the study patients present with symptomatic or incidental delayed pneumothorax after being discharged, these patients will be captured for analysis.

To help keep impartiality, in addition to the standard of care review of post biopsy chest x-rays, at a later time, all chest radiographs will be reviewed by an interventional radiologist who was not involved with the biopsy procedure and is unaware of the randomization arm. All disagreements will be solved based on consensus after a third impartial interventional radiologist reviews the images.

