12.0 CRITERIA FOR THERAPEUTIC RESPONSE/OUTCOME ASSESSMENT

Lack of any detectable pneumothorax as visualized on post procedure chest radiographs at 2 hours following the procedure is considered success. The rate of any pneumothorax that did not require treatment as well as those which require chest tube placement will be captured for analysis in each group.

Lack of prospective follow up chest x-ray at one week after biopsy will lower the accuracy of the study due to suboptimal capturing of delayed pneumothoraces by a phone call although this number is expected to be very low. For patients that are unable to be reached or unable to complete the follow up phone call, the incidence of a delayed pneumothorax and/or chest tube placement will be determined by a review of the patient's chart by the PI in the 2 weeks following the lung biopsy.

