14.0 BIOSTATISTICS

This is a randomized trial comparing autologous blood patch injection with BioSentry on the rate of pneumothorax after percutaneous lung biopsy. The primary endpoint is the rate of pneumothorax within 2 hours following biopsy. Pneumothorax is observed on post procedure CT scan or on follow-up chest radiographs while the patient is in the recovery room, according to standard of care.

This study will have a non-inferiority design to evaluate whether ABPI is associated with less than a 10% increase in pneumothorax rate compared to BioSentry. We will test the null hypothesis that ABPI is inferior, with a 10% or more increase in pneumothorax rate compared to BioSentry. The non-inferiority margin of 10% is considered clinically acceptable. Allowing for 1 interim assessment, the study will require 276 patients in each arm (552 patients total) to have 90% power to test this hypothesis. This sample size estimate assumes the pneumothorax rate with tract plug is approximately 20% based on a randomized study by Zaetta et al. An interim assessment will be performed after approximately half the patients (roughly 276 patients) have been enrolled onto the study. Using the Lan-DeMets spending function, the trial will terminate early for non-inferiority if with half the patients, a one-sided nominal Z-score of -2.538 ($p\text{-value} \leq 0.0056$) is observed. This nominal z-score will be recalculated based on the available exact information fraction at the time of the Data Safety Monitoring Board review. If the trial continues, the final assessment will use a Z-score of -1.662 with an associated $p\text{-value}$ of 0.0482. This preserves a 5% overall probability (1-sided type I error) of falsely concluding that ABPI is non-inferior to tract plug when it is truly worse. In 2012 IR service performed 1128 lung biopsies. IR service currently performs around 100 lung biopsies each month. With an anticipated eligibility rate of 50%, this study will take up to 24 months.

All randomized patients who undergo a biopsy will be analyzed for the primary outcome on a modified intent-to-treat basis according to the randomized treatment assignment regardless of the actual intervention received. The difference between pneumothorax rates for ABPI and BioSentry will be estimated and assessed using a Z-test. The same analysis method will be used to perform a secondary analysis on only patients who have a sealant placed after their biopsy.

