Secondary outcomes will include comparisons of ABPI with BioSentry on 1) delayed pneumothorax occurring after outpatient observation stay and within 2 weeks following lung biopsy, and 2) pneumothorax requiring chest tube placement up to 2 weeks following lung

biopsy. These outcomes will be assessed in a similar manner to the primary outcome. For patients that are unable to be reached or unable to complete the follow up phone call, the incidence of a delayed pneumothorax and/or chest tube placement will be determined by a review of the patient's chart by the PI in the 2 weeks following the lung biopsy.

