20.4 PHYSICIAN DATA FORM

Effect of Autologous Blood Patch Injection versus BioSentry hydrogel Tract Plug in the reduction of pneumothorax risk following lung biopsy procedures

1- Patient Demographics

MRN		Procedure date		/	/	
Last Name		Male	Female	DOB	/	/

2- Candidate for study Yes No

If no, please explain why or list/circle exclusion criteria #:

3- Consent obtained Yes No

4- Randomization # _____

5- Procedure parameters

Exclusion criteria

1. Passage through non-aerated lung or tissue OR Target lesion located LESS than 1.5 cm away from visceral pleura
2. Needle path transgressing pleural fissure or bleb
3. Coaxial technique not needed
4. Needle size 17 gauge
5. Prior ipsilateral lung interventions: biopsy, chest tube, surgery, radiation or pleurodesis

Target size (largest transverse diameter on reference image) _____ cm

Target depth (Needle path distance from pleura to outer edge of target) _____ cm

Lobe (please circle) RUL RML RLL LUL LLL

Position (please circle) Prone Other:

Type of biopsy (please circle) FNA Core Both

Number of biopsy samples FNA: Core:

6- Factors affecting outcome: Did you encounter (please circle)

More than 1 pleural puncture? Yes No

Passage through a fissure? Yes No

Complete passage through non aerated lung? Yes No

Passage through a bleb/bulla? Yes No

Usage of BARE needle WITHOUT coaxial system? Yes No

Intraprocedural pneumothorax? Yes No

Significant needle path hemorrhage within 2 cm of pleura? Yes No

7- Sealant technique used (please circle) Blood patch BioSentry None
 (Please note reason below)

8- Outcomes

Pneumothorax on CXR (please circle) Yes No

Pneumothorax - Second reader (please circle) Yes No

Chest tube placement (please circle) Yes No

Delayed complications (please circle) Yes No If Yes: _____

Notes:

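### Section 12.0 scores success on the film at 2 hours, while Sections 2.1, 4.3 and 14.0 count any pneumothorax within 2 hours; if 12.0 were the scoring rule, early events that clear would be lost, which favours non-inferiority

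*Combined protocol and SAP*

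**What the plan says.** All references are to the combined protocol and SAP.

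- **Section 12.0** (outcome assessment): "Lack of any detectable pneumothorax as visualized on post procedure chest radiographs at 2 hours following the procedure is considered success". Its next sentence says that untreated pneumothoraces and those needing a chest tube will be captured in each group. It does not say that a drained patient is a primary failure.
- **Section 2.1** (primary objective): the comparison is of ABPI and BioSentry "in reducing the rate of iatrogenic pneumothorax during the routine observation stay within 2 hours following image guided lung biopsy".
- **Section 14.0**: "The primary endpoint is the rate of pneumothorax within 2 hours following biopsy". On imaging: "Pneumothorax is observed on post procedure CT scan or on follow-up chest radiographs while the patient is in the recovery room".
- **Section 4.3**: "Any discernible pneumothorax on chest x-rays is considered a positive finding". It also counts a CT finding if it is larger than minuscule.
- **Section 10.0** (film schedule): "Two chest radiographs will be obtained immediately and 2 hours after the procedure as per standard of care". Sections 4.3 and 10.0 let chest tube placement follow from findings on post-procedure films and state no wait for the second film.
- **Section 14.0** (secondary outcome): "delayed pneumothorax occurring after outpatient observation stay and within 2 weeks following lung biopsy".
- **Section 20.4** (Physician Data Form): "Pneumothorax on CXR (please circle) Yes No", with a matching item for the second reader and a chest tube item. None of the three carries a time.

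**The concern.** Section 12.0, read literally, describes a state at one time point. Sections 2.1 and 14.0 describe an event that may occur at any time over two hours. The two rules give different answers for patients who can occur in this trial. One is a patient with a large pneumothorax on the immediate film who receives a chest tube and has a re-expanded lung at 2 hours. Another is a patient with a small early pneumothorax that is gone by 2 hours. Both are events under 2.1, 4.3 and 14.0, and both are successes under the wording of 12.0.

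The direction of the error matters in a non-inferiority trial. If the same proportion of events is removed from each arm, the absolute difference shrinks while the margin stays at 10 points, so an inferior sealant passes more easily. The interim look can also stop the trial for non-inferiority on the same count.

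There is a smaller problem at the other end of the window. Section 1.0 has patients monitored for at least two hours, so the stay can run longer. A pneumothorax first seen after 2 hours but before the stay ends is outside the primary window and, under 14.0, is not yet delayed.

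**Working it through.** **1. Reproduce the design.** Inputs from Section 14.0: 20% rate with the plug, 10-point margin, one-sided 5% error, 90% power, 276 per arm, boundaries 2.538 at half the information and 1.662 at the end (signs reversed here). Equal true rates are assumed for power.

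- Fixed design: n = (1.645 + 1.282)² × (0.20×0.80 + 0.20×0.80) / 0.10² ≈ 274.1, so 275 per arm.
- Two-look design: SE = √{[pB(1−pB) + pA(1−pA)]/276}, where B is BioSentry and A is ABPI; θ = [0.10 − (pA − pB)]/SE. The probability of declaring non-inferiority is 1 − P(Z₁ < 2.538 and Z₂ < 1.662), where Z₁ has mean θ√0.5, Z₂ has mean θ, both have unit variance, and their correlation is √0.5.
- With 20% in both arms: SE = 0.03405, θ = 2.937, probability 0.900. With 30% v 20%: θ = 0, probability 0.0500.

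The stated 276 per arm, 90% power and 5% error all reproduce.

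**2. A plausible range for lost events.** Let f be the share of within-2-hour pneumothoraces no longer visible on the 2-hour film. The documents do not give f. Section 3.0 gives an in-house rate of 23% with pneumothorax and 6.8% needing intervention: 6.8/23 = 29.6% of events treated. The share of treated cases clear by 2 hours is an assumption:

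- 25%: f = 0.25 × 29.6% = 7.4%
- 50%: f = 14.8%
- 75%: f = 22.2%

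A lower value of 5% is added. Early spontaneous resolution would add to f.

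**3. Effect at the margin.** True rates are 30% (ABPI) v 20% (BioSentry). Each is multiplied by (1 − f), with f equal in both arms.

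| f | ABPI v BioSentry as scored | Difference (points) | θ | P(declare non-inferiority) |
|---|---|---|---|---|
| 0 | 30.0% v 20.0% | 10.0 | 0 | 5.0% |
| 5% | 28.5% v 19.0% | 9.5 | 0.139 | 6.6% |
| 7.4% | 27.8% v 18.5% | 9.3 | 0.207 | 7.5% |
| 14.8% | 25.6% v 17.0% | 8.5 | 0.426 | 11.1% |
| 22.2% | 23.3% v 15.6% | 7.8 | 0.661 | 16.2% |

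**4. Sensitivity to the treated share.** The sealant data in Section 3.0 give smaller shares: 4/18 = 22% for the plug in its randomized study, and 2/12 = 17% for the in-house blood patch series. With half of treated cases clear by 2 hours, f = 11.1% and 8.3%. The difference becomes 8.9 and 9.2 points, and the false non-inferiority rate 9.2% and 7.9%.

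**5. Sample size.** Using the within-2-hour rule throughout leaves the 20% planning rate as it is, so 276 per arm stands.

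**The case against.** The strongest reply is that the rest of the plan already points one way. Section 14.0 is where the primary endpoint is named, its Z-test compares pneumothorax rates rather than 12.0 successes, and Sections 2.1 and 4.3 agree with it. Section 12.0 speaks of radiographs in the plural, and its next sentence treats drained cases as pneumothoraces. A statistician working from 14.0 would score early events correctly. This stands, and it makes the harm conditional.

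Section 10.0 also has all chest films re-read by a radiologist unaware of the arm, with a third reader for disagreements, and chest tubes are recorded. Misclassified patients could probably be recovered from stored films and charts. That also stands, but the re-read establishes what each film shows, not which film decides.

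Four stronger readings are tempting, and the documents do not support them:

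- **That the trial will score early events as successes.** This follows only if 12.0 overrides three other sections.
- **That the loss differs by arm because the operator knows the allocation.** This is possible, but nothing in the documents shows it.
- **That inpatients have no start point for delayed events.** Section 4.3 sends all patients to the same recovery unit with the same two films. The fault is mainly the loose word outpatient in 14.0.
- **That a scored difference below 10 points amounts to a non-inferiority claim.** The test must cross its boundary, which is why the working gives error rates.

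**Conclusion.** The inconsistency is real, concerns the primary endpoint, and is not resolved anywhere in the documents. The weight of the text favours the any-film, within-2-hours rule. The finding is therefore that one sentence in 12.0 conflicts with the rest, not that the planned analysis is known to be biased.

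If 12.0 were applied as written, the bias would favour non-inferiority under equal relative loss. For 5% to 22% of events lost, the one-sided error at the margin would be about 6.6% to 16%, against the stated 5%. This range rests on an assumed f, equal loss in both arms, and true rates of 30% v 20%. The documents do not allow the number of affected patients to be derived.

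The gap between the primary and delayed windows is a minor companion point; Section 1.0 puts delayed events below 1% of patients. Both should be settled before the interim analysis, since that look can end the trial.

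**What to change.** 1. **Section 12.0.** Rewrite the success sentence to match 14.0 and 4.3. A primary event is any pneumothorax discernible on any chest radiograph up to and including the 2-hour film, or larger than minuscule on post-procedure CT. A patient drained for pneumothorax before the 2-hour film is scored as an event whatever that film shows. The CT clause must stay; a radiograph-only sentence would create a new conflict with 4.3 and 14.0.
2. **Pneumothorax before sealant deployment.** Keep these patients in the primary analysis, as Section 4.3 already states.
3. **Section 14.0, delayed pneumothorax.** Start the delayed window where the primary window ends, for inpatients and outpatients alike, so that no event falls between the two.
4. **Physician Data Form.** Record which film was positive (immediate, or later up to 2 hours) and whether drainage came before the 2-hour film.

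The cost is a few sentences and a split form item. The change concerns scoring only: 276 per arm is unaffected, and no new films, visits, readers or changes to clinical management are needed.

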13.0 CRITERIA FOR REMOVAL FROM STUDY

Patient exclusion will be performed after chart review and interview. Patients will be excluded from the study in the event the patient was found to have a history of prior ipsilateral lung intervention as outlined above. Once randomized, patients will be included in the intent to treat analysis whether they received a blood patch/BioSentry plug or not.

14.0 BIOSTATISTICS

This is a randomized trial comparing autologous blood patch injection with BioSentry on the rate of pneumothorax after percutaneous lung biopsy. The primary endpoint is the rate of pneumothorax within 2 hours following biopsy. Pneumothorax is observed on post procedure CT scan or on follow-up chest radiographs while the patient is in the recovery room, according to standard of care.

This study will have a non-inferiority design to evaluate whether ABPI is associated with less than a 10% increase in pneumothorax rate compared to BioSentry. We will test the null hypothesis that ABPI is inferior, with a 10% or more increase in pneumothorax rate compared to BioSentry. The non-inferiority margin of 10% is considered clinically acceptable. Allowing for 1 interim assessment, the study will require 276 patients in each arm (552 patients total) to have 90% power to test this hypothesis. This sample size estimate assumes the pneumothorax rate with tract plug is approximately 20% based on a randomized study by Zaetta et al. An interim assessment will be performed after approximately half the patients (roughly 276 patients) have been enrolled onto the study. Using the Lan-DeMets spending function, the trial will terminate early for non-inferiority if with half the patients, a one-sided nominal Z-score of -2.538 ($p\text{-value} \leq 0.0056$) is observed. This nominal z-score will be recalculated based on the available exact information fraction at the time of the Data Safety Monitoring Board review. If the trial continues, the final assessment will use a Z-score of -1.662 with an associated $p\text{-value}$ of 0.0482. This preserves a 5% overall probability (1-sided type I error) of falsely concluding that ABPI is non-inferior to tract plug when it is truly worse. In 2012 IR service performed 1128 lung biopsies. IR service currently performs around 100 lung biopsies each month. With an anticipated eligibility rate of 50%, this study will take up to 24 months.

All randomized patients who undergo a biopsy will be analyzed for the primary outcome on a modified intent-to-treat basis according to the randomized treatment assignment regardless of the actual intervention received. The difference between pneumothorax rates for ABPI and BioSentry will be estimated and assessed using a Z-test. The same analysis method will be used to perform a secondary analysis on only patients who have a sealant placed after their biopsy.

Secondary outcomes will include comparisons of ABPI with BioSentry on 1) delayed pneumothorax occurring after outpatient observation stay and within 2 weeks following lung biopsy, and 2) pneumothorax requiring chest tube placement up to 2 weeks following lung

biopsy. These outcomes will be assessed in a similar manner to the primary outcome. For patients that are unable to be reached or unable to complete the follow up phone call, the incidence of a delayed pneumothorax and/or chest tube placement will be determined by a review of the patient's chart by the PI in the 2 weeks following the lung biopsy.

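### Section 14.0 updates the interim boundary for the actual information fraction but fixes the final boundary at -1.662, so a look later than half slightly exceeds the stated 5% one-sided error

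*Combined protocol and SAP*

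**What the plan says.** All of the relevant text is in section 14.0 (Biostatistics).

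- Timing: "An interim assessment will be performed after approximately half the patients (roughly 276 patients) have been enrolled onto the study".
- Interim boundary: under a Lan-DeMets spending function whose family is not named, the trial stops for non-inferiority at half the patients if Z reaches -2.538 (one-sided p of 0.0056 or less).
- Update rule: "This nominal z-score will be recalculated based on the available exact information fraction at the time of the Data Safety Monitoring Board review". At that point in the text -2.538 is the only Z-score that has been introduced, so the rule refers to the interim value.
- Final boundary: "If the trial continues, the final assessment will use a Z-score of -1.662", with p = 0.0482.
- Claimed property: "This preserves a 5% overall probability (1-sided type I error) of falsely concluding that ABPI is non-inferior to tract plug" when it is truly worse.

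No other part of the document says that the final boundary will be updated.

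**The concern.** In a two-look design with alpha spending, the final critical value depends on two things: how much alpha was spent at the interim, and the correlation between the interim and final statistics. Both change with the information fraction t. The plan expects t to differ somewhat from one half, since it describes the timing as approximate and provides for recalculating the interim value. If only that value moves, the pair no longer matches. A later look spends more alpha at the interim, and an unchanged final cutoff does not give that alpha back.

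The threshold at stake decides the primary non-inferiority claim, and the document states a 5% error rate for it. A final Z lying between -1.662 and the matching boundary would be declared non-inferior under the plan as written, but not under a rule that keeps 5%. If this had to be settled after the data were seen, either choice would be open to dispute.

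**Working it through.** **Inputs (section 14.0).** Overall one-sided alpha 0.05; 276 per arm, 552 in total; 90% power; pneumothorax rate 20% in the plug arm, taken as 20% in both arms for power; margin 10 percentage points; interim at about 276 patients; boundaries -2.538 and -1.662. Boundaries are shown below as absolute values.

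**Assumptions.** The spending family is O'Brien-Fleming type, t is interim information divided by final analysed information, and the final boundary is read literally as fixed.

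**Formulas.**
- Alpha spent by the interim: a(t) = 2[1 - Phi(1.960/sqrt(t))].
- Interim boundary: c1 = Phi^-1(1 - a(t)).
- Overall error: a(t) + P(Z1 < c1, Z2 >= c2), where Z1 and Z2 are standard bivariate normal with correlation sqrt(t).
- Matching final boundary: the c2 that makes the overall error 0.05.

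**Step 1: reproduce the plan's figures at t = 0.50.**
- 1.960/sqrt(0.50) = 2.772, so a(0.50) = 0.00557 and c1 = 2.538. This agrees with the plan.
- Solving for the final value gives c2 = 1.6621, p = 0.0482. This agrees with the plan.
- The printed pair gives an overall error of 5.00%.
- A Pocock-type spending function would give an interim value of 1.866, which does not fit. The O'Brien-Fleming type is therefore inferred.
- Sample size: a fixed design needs 274.04 per arm before rounding. Multiplying by the group-sequential inflation factor 1.0071 gives 275.99, hence 276. Power with 276 per arm is 90.0%.

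**Step 2: move the look, recalculate c1, hold c2 at 1.662.**

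| t | alpha spent at interim | c1 | overall error with c2 = 1.662 | c2 that restores 5% |
|---|---|---|---|---|
| 0.40 | 0.0019 | 2.887 | 4.89% | 1.651 |
| 0.45 | 0.0035 | 2.699 | 4.94% | 1.656 |
| 0.50 | 0.0056 | 2.538 | 5.00% | 1.662 |
| 0.51 | 0.0061 | 2.509 | 5.02% | 1.664 |
| 0.55 | 0.0082 | 2.399 | 5.08% | 1.670 |
| 0.60 | 0.0114 | 2.277 | 5.16% | 1.680 |
| 0.75 | 0.0236 | 1.984 | 5.44% | 1.715 |

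Below half the error is under 5%; above half it is over 5%.

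**Step 3: how far from half could the look fall?** The documents give no review delay, so this step is an illustration under assumption. At the planned pace of 552/24 = 23 patients a month, a two-month delay gives (276 + 46)/552 = 0.58 and an error of about 5.13%. A six-month delay gives (276 + 138)/552 = 0.75 and 5.44%. Both require every patient enrolled by the review to be in the data cut.

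**Step 4: effect of the fix on power.** The drift is 0.10/sqrt(2 x 0.20 x 0.80/276) = 2.937. With c1 = 2.277 and c2 = 1.680 at t = 0.60, power is 89.8%, against 90.0% at t = 0.50.

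**The case against.** The strongest defence is that the plan names its method. Under Lan-DeMets spending the final boundary follows from the alpha already spent, so -1.662 can be read as the value for the planned case, just as -2.538 is, and a statistician applying the method would update both. Part of this stands: the document does not forbid updating the final value. But it gives an explicit update rule for one boundary, a fixed value for the other, and then states the 5% property for that pair. The text as written should not depend on the reader's repair.

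The second defence is size, and it stands. Between t = 0.51 and 0.60 the excess is about 0.02 to 0.16 percentage points. For comparison, an exact binomial calculation for an unpooled Z-test (the plan says only that a Z-test is used) with 276 per arm and cutoff 1.662 gives a size of 4.87% at 20% versus 30% and 4.94% at 15% versus 25%, against a nominal 4.82%. The normal approximation alone therefore moves the error by 0.05 to 0.12 points. The primary outcome is also known within two hours, so a data cut at about 276 patients would keep t near one half however late the board meets.

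Three stronger readings are tempting and should be set aside:

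- A reader might infer that 5% is protected only if the look is at exactly half. It is not so: any look before half keeps the error below 5%.
- A reader might infer that the boundaries were miscalculated. All the printed values reproduce at t = 0.50.
- A reader might infer an inflation approaching half a percentage point. That needs a look near t = 0.75, far from the planned timing, and a delay that no section states.

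**Conclusion.** The point holds as a minor gap in the decision rule. Read literally, section 14.0 matches its stated 5% exactly only at t = 0.50; it is slightly conservative before half and slightly anti-conservative after it, reaching 5.08% at t = 0.55 and 5.16% at t = 0.60. At t = 0.60 the trial's conclusion would differ only for a final Z between -1.662 and -1.680.

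The sizes depend on the inferred O'Brien-Fleming-type family and on the literal reading of the final boundary as fixed. The direction of the error after a late look does not depend on any assumed review delay. The final information may also differ from plan, because the primary analysis covers only randomized patients who undergo a biopsy; this is a further reason to define t by the information actually analysed.

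**What to change.** Replace the sentence that fixes the final boundary with wording such as: *If the trial continues, the final boundary will be recalculated from the same Lan-DeMets (O'Brien-Fleming-type) spending function, using the alpha actually spent at the interim and the actual ratio of interim to final information. It equals -1.662 (p = 0.0482) if the interim is at exactly half.* The 5% statement that follows is then true for any timing of the look, subject to the normal approximation, and the spending family is named.

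The cost is one sentence, with no change to sample size or conduct. The final threshold becomes slightly stricter after a late look (-1.680 at t = 0.60, with power about 89.8%) and slightly more lenient after a look before half (-1.651 at t = 0.40).
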